### 8.1 Discontinuation of Trial Vaccine Administration

The primary reason for discontinuation of further administrations of trial vaccine doses will be recorded in the subject's eCRF according to the following categories:

- Consent withdrawal by the subject.

The reason for withdrawal, if provided, should be recorded in the eCRF.

Note: All attempts should be made to determine the underlying reason for the withdrawal and, where possible, the primary underlying reason should be recorded (i.e., withdrawal due to an AE should not be recorded in the "voluntary withdrawal" category).

- AE (including known side effects of the trial vaccine).

If discontinuation is due to an AE possibly related to the trial vaccine or trial procedures, the subject must be followed up by additional examinations according to the medical judgment of the Investigator until the condition is resolved or the Investigator deems further observations or examinations to be no longer medically indicated.

- Change in the subject's overall medical status prohibiting further participation.
- Pregnancy (see Section 9.1.2).

Any subject who, despite the requirement for adequate contraception, becomes pregnant during the trial will not receive further trial vaccine doses. The site should maintain contact with the pregnant subject and complete a "Clinical Trial Pregnancy Form" as soon as possible. In addition, the subject should be followed up until the birth of the child, or spontaneous or voluntary termination. When pregnancy outcome information becomes available, the information should be captured using the same form. The subject should be reported as an IMP discontinuation and the reason (i.e., pregnancy) should be given.

- SARS-CoV-2 infection, virologically confirmed by positive RT-PCR test (as specified in Table 1).

Note: Subjects who develop laboratory-confirmed COVID-19 after the first vaccine dose administration should only receive the second vaccine dose 2 weeks after getting fully recovered and if it falls under the time windows (see Section 6.4).

- Trial terminated by the Sponsor (in which case the minimum safety follow-up of 1 year after the last trial vaccine dose would be performed).
- Major protocol deviation.
- Wants to receive authorized/licensed vaccine.
- Other.

Note: The specific reasons should be recorded in the “specify” field of the eCRF.

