6.4 Changes to Protocol from Version 2.0 to Protocol Amendment #1

- For this study an abbreviated CSR will be produced due to the reduced sample size. The CSR will be based on the reduced scope (see Appendix 4 List of Abbreviated Scope Based on SAP Version 2.0). For the primary safety endpoints, key analysis will be included related to summary/occurrence of solicited adverse events, duration of solicited adverse events, unsolicited adverse events, adverse events of special interest and adverse events leading to either study or vaccine withdrawal.
- The analysis of number and percentage of subjects with Grade 3 adverse reactions or SAE considered related to the trial vaccine according to the investigator with 95% credibility intervals on the beta (0.5, 1.5) prior distribution and estimate will not be performed due to the small number of subjects.
- For the secondary immunogenicity endpoints, the immunogenicity set was planned for Day 1 (baseline), Day 29, Day 120, Day 211 and Day 393. Instead, the analysis will be performed with per protocol immunogenicity set for all available time points (Day 1(baseline), Day 29, Day 43 and Day 120).
- Exploratory endpoints related to CMI response: these analyses will not be finalized due to invalid samples and small sample size.
- Exploratory endpoints related to occurrence of confirmed COVID-19 cases: analysis will not be performed.
- Only time points up to Day 120 will be included.

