7.0 Trial Objectives

All objectives, with the exception of the exploratory objectives related to CMI response, will be analyzed in all subjects overall, as well as per underlying co-morbidity.

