
Occurrence of confirmed COVID-19 cases
 
Number of subjects with reverse transcription polymerase chain reaction (RT-PCR)-confirmed SARS-CoV-2 infection as measured by RT-PCR at clinically determined time points throughout the trial.
 
Number of subjects with asymptomatic SARS-CoV-2 infection as measured by serological titers of nucleocapsid antibodies on Day 1, Day 43, Day 120 and Day 393.
	
In subjects who received at least one dose of CVnCoV vaccine and a post baseline vaccine safety assessment is available. Subjects receiving an authorized/licensed COVID-19 vaccine during the course of the trial will be censored at the day after intake.
 
Number and percentage of subjects by co-morbidity at baseline and post-baseline time points with a positive RT-PCR result. This exploratory endpoint will be analyzed with the safety analysis set.
 
Number and percentage of subjects by co-morbidity at baseline and post-baseline with a positive RT-PCR result and/or infection defined by SARS-CoV-2 N-antigen and no COVID-19 symptoms. This exploratory endpoint will be analyzed with the immunogenicity set. Day 211 and Day 393 will not be measured.

	
CMI responses will not be analysed.

ENDPOINTS (subject level)	ESTIMANDS (population level)

CMI response
 
On Day 1, Day 29, Day 43 and Day 120 in peripheral blood stimulated with antigen in a subset of subjects*:
 
The SARS-CoV-2 S-specific T cell response, as measured by cytokine and chemokine expression after antigen stimulation using a standardized whole blood collection and culture system.
	

* The subset of subjects to participate in neutralizing activity and CMI response testing shall consist of approximately 25 subjects for each co-morbidity (up to a maximum of 175 subjects).

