9.5.2 Per Protocol Immunogenicity Subset (PPI)

The Per Protocol Immunogenicity subset (PPI) will include all subjects who:

- Received both doses within the windows defined in the protocol.
- Have no important protocol deviations expected to impact the immunogenicity outcomes as specified in the statistical analysis plan (SAP).
- Have not received medical treatments (such as blood products, immunoglobulin therapy) that may interfere with any of the proposed immunogenicity measurements.
- Have at least 1 blood sample collected starting at 14 days (Day 43) post-second vaccination available for analysis.

The PPI will be the primary analysis population for SARS-CoV-2 RBD of S protein antibody responses and SARS-CoV-2 viral neutralizing antibody responses.

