12.7.3 Exploratory Endpoints

The below mentioned exploratory endpoints will be included in the abbreviated scope. Cell-mediated immune response and cytokine concentrations will not be included.

- Number of subjects and percentages with RT-PCR-confirmed SARS-CoV-2 infection at clinically determined time points throughout the trial will be tabulated by time point. This table and listing will be presented for the safety set.
- Number of subjects and percentages with asymptomatic SARS-CoV-2 infection as measured by serological titers of nucleocapsid antibodies on day 1, day 43 and day 120 will be tabulated by time point. Subjects with COVID-19 symptoms are excluded.

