14.2 Immunogenicity
Table 14.2.1.1 Seroconversion Rate for SARS-CoV-2 RBD Antibodies (IgG) by Time Point (Per Protocol Immunogenicity Set)
Table 14.2.2.1 Summary of SARS-CoV-2 RBD Antibodies (IgG) by Time Point (Per Protocol Immunogenicity Set)
Table 14.2.3.1 Seroconversion Rate for SARS-CoV-2 neutralizing Antibodies MN 25 TCID50 by Time Point (Per Protocol Immunogenicity Set)
Table 14.2.4.1 Summary of SARS-CoV-2 neutralizing Antibodies MN 25 TCID50 in Serum at Day 43 (Per Protocol Immunogenicity Set)
Table 14.2.6.1 Subjects with Asymptomatic SARS-CoV-2 infection as measured with retrospective Serology on Day 1, 43, 120 (Per Protocol Immunogenicity Set)

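### The SAP both drops and keeps the COVID-19 infection analyses, and the one infection table in Appendix 4 uses the per-protocol set, which excludes all one-dose subjects

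*SAP*

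**What the plan says.** SAP 6.4 lists what changes in the abbreviated report. On infection it reads: "Exploratory endpoints related to occurrence of confirmed COVID-19 cases: analysis will not be performed".

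Three other places in the SAP point the other way:

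- SAP 7.0 begins: "All objectives, with the exception of the exploratory objectives related to CMI response, will be analyzed in all subjects overall". Only cell-mediated immunity (CMI) is exempted. SAP 7.3 keeps one exploratory objective: how often laboratory-confirmed COVID-19 occurs following one dose and following two.
- SAP 12.7.3 opens: "The below mentioned exploratory endpoints will be included in the abbreviated scope". It then lists RT-PCR-confirmed infection and asymptomatic infection measured by nucleocapsid (N protein) serology. Of the RT-PCR output it says: "This table and listing will be presented for the safety set".
- SAP 9.4 gives RT-PCR-confirmed infection to the safety analysis set. Of asymptomatic infection it says: "This exploratory endpoint will be analyzed with the immunogenicity set".

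Appendix 4, the list of outputs to be produced, has one infection table: "Table 14.2.6.1 Subjects with Asymptomatic SARS-CoV-2 infection as measured with retrospective Serology on Day 1, 43, 120 (Per Protocol Immunogenicity Set". It has no RT-PCR table. Its listings are 16.2.6.7 (RT-PCR-confirmed, Safety Analysis Set), 16.2.6.8 (asymptomatic, Immunogenicity Set) and 16.2.6.9 (COVID-19 symptoms, Safety Analysis Set).

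The first condition for the per protocol immunogenicity subset (PPI), in SAP 9.5.2, is: "Received both doses within the windows defined in the protocol". The immunogenicity set (SAP 9.5.1) needs only one dose, a baseline sample and one further sample.

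**The concern.** A programmer working from this SAP cannot tell whether the two infection endpoints are to be tabulated. Whichever instruction is followed, the study report departs from another part of the plan.

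The choice of analysis set matters separately. The exploratory objective asks about infection after one dose as well as after two. A table on the PPI has no one-dose subjects in its counts or its denominators, so it can answer only for subjects who completed the schedule in window. One-dose subjects are expected here: the amendment's Table 1 has a row for those whose last injection was on Day 1. Nothing in the SAP explains why this endpoint was moved to the PPI. SAP 6.4 makes that move only for the secondary immunogenicity endpoints, and the sentence in SAP 12.7.2 dropping analyses on the immunogenicity set concerns the humoral response.

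**Working it through.** The plan states no figure to reproduce, so the check is mainly a comparison of text.

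**1. What each place says about each endpoint**

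| Source | RT-PCR-confirmed infection | Asymptomatic infection |
|---|---|---|
| SAP 6.4 | Not analysed | Not analysed, because 9.4 puts it under the same confirmed-case heading |
| SAP 7.0 | Kept (only CMI exempted) | Kept (only CMI exempted) |
| SAP 9.4 | Safety analysis set | Immunogenicity set |
| SAP 12.7.3 | Table and listing, safety set | Table at Days 1, 43 and 120; no set named |
| Appendix 4, tables | None | 14.2.6.1, PPI |
| Appendix 4, listings | 16.2.6.7, Safety Analysis Set | 16.2.6.8, Immunogenicity Set |

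Appendix 4 departs from 6.4 by keeping an infection table. It departs from 12.7.3 by having no RT-PCR table, and from 9.4 by using the PPI.

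**2. Is 12.7.3 leftover text?** No. It refers to the abbreviated scope, removes CMI and omits Day 393. SAP 12.7 marks dropped analyses with an asterisk, and neither bullet in 12.7.3 has one.

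**3. Who is outside Table 14.2.6.1?** All one-dose subjects, by the first PPI condition. SAP 6.3 gives 129 enrolled, with no split by number of doses. Under an assumed one-dose share of 10% to 40%:

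- 129 × 0.10 = 12.9, about 13 subjects
- 129 × 0.40 = 51.6, about 52 subjects

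These are subjects outside the table, not missed infections.

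**4. Which of their samples are lost?** In the amended schedule, N-protein sampling falls on Day 43, Day 120 and the end-of-trial visit. For a subject last injected on Day 1, the end-of-trial visit is Day 91. That day is not among the table's time points, so a change of analysis set alone would still leave the sample out. Day 91 is within the limit of Day 120 set in SAP 6.4.

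**5. Does the PPI selectively lose infected subjects?** The possible route is a second dose missed or out of window after a confirmed infection. The Day 29 window is −3/+14 days:

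- Earliest dose 2: 29 − 3 = Day 26. Latest: 29 + 14 = Day 43.
- Protocol 9.3 places dose 2 two weeks after complete recovery, so the latest recovery is 43 − 14 = Day 29.
- With L days from onset to recovery (assumed), the latest onset is Day 29 − L.
- If onset is uniform over Days 2 to 29 (28 days, assumed), the share that misses the window is L/28.

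| L (days) | Latest onset | Share missing the window |
|---|---|---|
| 3 | Day 26 | 3/28 = 11% |
| 7 | Day 22 | 7/28 = 25% |
| 10 | Day 19 | 10/28 = 36% |
| 14 | Day 15 | 14/28 = 50% |
| 21 | Day 8 | 21/28 = 75% |

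This loss would matter for an RT-PCR table on the PPI, but none is planned. It concerns symptomatic cases, because swabs are triggered by symptoms. SAP 12.7.3 removes symptomatic subjects from the asymptomatic table in any analysis set. Asymptomatic infection prompts no swab, and the first N-protein sample after baseline is at Day 43, after the nominal second dose. It would therefore not normally delay dose 2.

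**The case against.** **The SAP may resolve itself.** SAP 6.3 says the planned analyses of version 1.0 stay in the text and the changes are in Appendix 4. SAP 9.4 and 12.7 both refer to 6.4 and Appendix 4 for the reduced scope. If 6.4 is read as covering only RT-PCR-confirmed cases, Appendix 4 would agree with it. This narrows the conflict mainly to 6.4 against 12.7.3, but does not remove it. SAP 12.7.3 was rewritten for the abbreviated scope and promises an RT-PCR table that Appendix 4 lacks. SAP 9.4 and Protocol 4.2.3 place both endpoints under one confirmed-case heading. The mismatch in analysis set remains on any reading.

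**A reader might infer that a count on the PPI is biased low because infected subjects drop out of it.** The documents do not support that for Table 14.2.6.1, for the reasons in step 5. A narrow route remains. SAP 10.7.8 counts a positive PCR without a COVID-19 event of special interest as asymptomatic infection, and Protocol 8.1 lists among reasons for discontinuing vaccination "SARS-CoV-2 infection, virologically confirmed by positive RT-PCR test (as specified in Table 1". No frequency is given for this, and no infection counts are given at all.

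**A reader might also infer that under 6.4 the objective gets no analysis.** That goes too far. COVID-19 is on the list of adverse events of special interest (AESIs), and Table 14.3.2.26.1 tabulates those for the whole trial on the Safety Analysis Set. Listings 16.2.6.7 to 16.2.6.9 show individual data on sets that admit one-dose subjects. Even so, a table by preferred term does not show RT-PCR confirmation by time point, and a listing gives no rate.

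**The gain may be modest.** These outputs are exploratory and descriptive, in a halted trial. The amended schedule also stops immunogenicity blood draws once a subject has an authorised vaccine, so some one-dose subjects will have no later N-protein sample. Both points stand and limit the consequence.

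**Conclusion.** The concern holds as a conflict within the current SAP and a mismatch of analysis set. SAP 6.4 and 12.7.3 give opposite instructions, Appendix 4 carries out neither, and Table 14.2.6.1 is on the PPI against SAP 9.4 and its own companion listing. As listed, the table cannot describe infection after a single dose.

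The numerical effect cannot be fixed from the documents. It depends on how many of the 129 had one dose and how many of those have an N-protein sample after baseline, and neither is stated. The 13 to 52 range rests wholly on the assumed 10% to 40%. No direction of bias in the asymptomatic count is shown, and nothing here affects the primary or secondary endpoints.

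**What to change.** Make one decision for each of the two endpoints and state it identically in SAP 6.4, 7.0/7.3, 9.4, 12.7.3 and Appendix 4. The documents do not show which statement reflects the sponsor's intention, although most of the current text indicates that both endpoints are kept. If so:

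- remove the COVID-19 line from SAP 6.4;
- add an RT-PCR-confirmed infection table on the Safety Analysis Set, as 12.7.3 states;
- run Table 14.2.6.1 on the immunogenicity set, as 9.4 states;
- add the Day 91 end-of-trial N-protein sample of one-dose subjects to that table's time points, and show how many subjects have a result at each time point.

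If the endpoints are dropped, delete Table 14.2.6.1 and align 7.0/7.3, 9.4 and 12.7.3 with 6.4.

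The cost of keeping them is SAP wording, one changed population, one added time point and one short table, using samples already scheduled and data already listed.

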7.0 Trial Objectives

All objectives, with the exception of the exploratory objectives related to CMI response, will be analyzed in all subjects overall, as well as per underlying co-morbidity.

7.1 Primary Objectives

- To evaluate the safety and reactogenicity profile after 1 and 2 dose administrations of CVnCoV.
- To evaluate the humoral immune responses 14 days after 2 dose administrations of CVnCoV.

7.2 Secondary Objective

- To evaluate the humoral immune responses after 1 and 2 dose administrations of CVnCoV at different time points during the trial.

7.3 Exploratory Objectives

- To evaluate the occurrence of laboratory-confirmed cases of COVID-19 after 1 and 2 doses of CVnCoV.

8.0 Trial Design

8.1 Overall Design

This is a Phase 3 open-label, single-arm trial to assess the safety, reactogenicity and immunogenicity of CVnCoV in an adult population with co-morbidities known to increase the risk for (severe) COVID-19. The selected co-morbidities which will be investigated are obesity, chronic cardiovascular disease, chronic kidney disease, chronic obstructive pulmonary disease (COPD), human immunodeficiency virus (HIV) infection, type 2 diabetes mellitus and post-renal transplantation.

Male and female subjects ≥ 18 years of age with 1 or more of the above co-morbidities will be eligible for the trial, with a life expectancy of at least 1 year as per the Investigator's assessment. Eligible subjects at screening must have no overt clinical symptoms or signs of COVID-19.

Subjects will be enrolled into 1 trial group:

- CVnCoV ($n = 1,200$): CVnCoV 12 μ g on Day 1 and Day 29.

The CVnCoV dose level to be administered in this trial was selected based on data from trial CV-NCOV-001 and confirmed in trial CV-NCOV-002. The 12- μ g dose level is currently being investigated in large-scale Phase 2b/3 trials in subjects > 18 years of age, both in subjects in the CV-NCOV-004 "Herald" trial and also in health care workers in the CV-NCOV-005 trial.

The trial contains 10 protocol-scheduled visits and 2 protocol-scheduled phone contacts. In addition, there will be a protocol-scheduled safety contact to collect diary card data on Day 9 for the first 25 subjects enrolled in the co-morbidities chronic kidney disease, COPD, chronic cardiovascular disease and diabetes mellitus (see below for details on the stratification).

Stratification Based on Co-Morbidities

For chronic kidney disease, COPD, chronic cardiovascular disease and diabetes mellitus, the first 25 subjects enrolled in each co-morbidity will be restricted to those with mild to moderate disease.

These first 25 subjects per co-morbidity will be followed up for safety and reactogenicity for at least 1 week after the first dose. An assessment of these data will be performed by CureVac's internal Safety Review Committee (iSRC) and DSMB Chair overviewing the clinical development program of CVnCoV. Once the safety of CVnCoV has been assessed in these 25 subjects and following iSRC and DSMB Chair approval, subjects with more severe forms of the co-morbidity may be enrolled as per the Investigator's decision.

For obesity, HIV and renal transplant, no distinction will be made between the initial 25 subjects that can be enrolled and any further enrollments. As described above, for subjects with multiple high-risk co-morbidities, the subject's main medical condition as determined by the Investigator will be used for enrollment stratification. A minimum of at least 50 subjects will be enrolled in each co-morbidity with a maximum of ~ 200 subjects.

8.2 Stopping/Pausing Rules for Safety

8.2.1 Individual Subjects Stopping Rules

Individual stopping adverse events (AE) rules will be applicable during the entire trial to ensure safe administration of the second dose to subjects vaccinated with the first vaccine dose.

Individual subject stopping rules are met in case any of the following events occur on the day of vaccination or the following 7 days (Days 1-8):

- An allergic/anaphylactic reaction considered as related to the trial vaccine.

- Any SAE considered as related to the trial vaccine.
- Any Grade 3 AE considered as related to the trial vaccine, with the following exceptions:
 - Transient Grade 3 systemic AE (fever, headache, fatigue, chills, myalgia, arthralgia, nausea/vomiting and diarrhea) considered as related to the trial vaccine that resolved within 24 hours to Grade ≤2

If any of these rules are met, the subject must not receive the second vaccine dose. The subject will be encouraged to continue participation until the end of the trial for safety and immunogenicity assessments.

8.2.2 Pausing of the Trial

The decision to pause the trial (i.e., temporary stopping of enrollment and vaccinations) due to a safety signal (see section 6.1 for more details for other reasons) will be based on a recommendation from the DSMB in consultation with the Sponsor. The DSMB may recommend pausing the trial for a safety concern following a review of accumulating safety data presented at the regularly scheduled DSMB meetings or from an ongoing review of AEs, which include but are not limited to, suspected unexpected serious adverse reactions (SUSARs); all SAEs judged as related to trial vaccine; concerning SAEs (e.g., adverse events of special interest (AESIs)); and all life-threatening SAEs and deaths. These events will be monitored by the DSMB (which is for entire COVID-19 vaccine clinical development trials encompassing CV-NCOV-001, -002, -004, -005 and -003) on a regular basis during the trial. The selected AEs and procedures for the safety review are described in detail in the DSMB Charter.

To ensure subject safety on an ongoing basis, a listing of the AEs as described above will be routinely monitored by the Chair of the DSMB (or designee) at regular intervals. For each review, the Chair [or designee(s)] will determine whether any single event or group of events constitute a new safety signal. If not, the Chair will inform the Trial Team that there are no safety concerns. Conversely, if there is a safety concern, the Chair may convene an ad-hoc DSMB meeting for further assessment of the event(s).

An iSRC will review the AEs across the clinical trials on a weekly basis and the meeting minutes will be shared with the DSMB Chair.

Based on the assessment of the benefit-risk ratio and biologic plausibility of a causal relationship of the AE(s) to the trial vaccine, the DSMB will make a recommendation to the Sponsor to either continue the trial as planned, modify its conduct, or pause the trial to allow further evaluation of the AE(s). If the latter, the Sponsor will make the decision to pause the trial in consultation with the DSMB.

Please refer to the DSMB Charter for additional discussion of the DSMB's role and responsibilities.

Details on the composition, objectives, and responsibilities of the DSMB, and the schedule and conduct of the DSMB meetings will be described in the DSMB Charter.

